#### 4. Research Plan / Description of the Research Methods:

**4.a.** Provide a **comprehensive narrative** describing the **research methods**.

- 1) Provide the order in which tests/procedures will be performed,
- 2) Provide the setting for these events and a description of the methods used to protect privacy during the study.
- 3) Provide the plan for data analysis (include as applicable the sample size calculation)

Please respond to all components of this item, or clearly indicate which components are not applicable.

As standard of care evaluation of POTS, patients will be evaluated with autonomic testing, pupillometry, supine and standing catecholamine levels, serological testing, and standing vitals. Skin biopsy (for determination of intraepidermal nerve fiber density) can be included at the discretion of PI in selected cases, Standard of care autonomic testing includes QSART testing, heart rate variability testing (via ECG), continuous blood pressure recording, Head Up Tilt Test, and pupil testing. Patients will also complete several surveys including COMPASS-31, Quality of Life questionnaire and fatigue symptom score.

Those patients with clinical features of autoimmunity will be eligible to enroll in the treatment study. Consenting patients will be assigned randomly to one of two groups. Both groups will receive both IVIG and albumin infusions (0.4 gm/kg). One group will receive IVIG infusions every week for 4 weeks then every 2 weeks for an additional 8 weeks (12 weeks total) followed by albumin infusions weekly for 4 weeks then every 2 weeks for 8 weeks (12 weeks total). There will be a 6 week washout and evaluation period between the treatment phases. The second group will receive albumin infusions first followed by IVIG infusions.

We will be following the Aston infusion center IVIG solution Infusion order. Patients will receive premedication's with 10mg of Cetirizine (Zyrtec) by mouth and 500 mg Acetaminophen (Tylenol) by mouth 30 min. (+/- 5 min) prior to infusion. After premedication and placement of peripheral IV, they will receive D5W 25 mL IV at 300 mL/hour (immediately before infusion). Then the patients will receive study medication in a blinded fashion. The dose of medication will be 0.4 g/kg (either Gammunex-C, 10% or Albumin, 10%). The dose will be rounded to the nearest 5 grams, and the dose will remain constant for each of the 8 study infusions even if weight changes. Since albumin is packaged at a 20% solution, this drug will be diluted to 10% using D5W prior to infusion. The prepared study drug dose will be provided by the research pharmacist in packaging marked with the study subject identifier and infusion number but will have no identifiers to indicate the drug identity (infusion nurse, patient and study coordinator must remain blinded to the treatment assignment). Infusion rate will start at 0.6 ml/kg/hour and may be increased by 0.6 ml/kg/hour every 15 min as, tolerated, to a maximum infusion rate of 210 ml/hour. Subsequent infusion rates may be started at the tolerated rate. Start and stop times and infusion rates will be recorded in the study log. Vital signs will be recorded at the start and end of the infusion and at the time of any changes of infusion rate or clinical symptoms. Once the study infusion is complete, the infusion nurse will alert the study coordinator, and the coordinator will check on the patient for any emergent AEs.

Post infusion, the intravenous catheter will be flushed with D5W 25 mL IV at 300 ml/hour and then the catheter will be removed. Once the coordinator check is complete the patient can be discharged.

Neither the patient nor the examiner will know if they are receiving IVIG or albumin until after the study is over. Patients in the study will be asked to complete a diary entry every day during the duration of the study (includes fluid intake, minutes of exercise, daily symptom score, and perceived side effects). More detailed assessment will be made at beginning, mid-point washout and end of study with including stand test, supine and standing catecholamine levels, COMPASS-31, fatigue score, quality of life score and symptom scores. Skin biopsy will be repeated at the assessment if the biopsy was performed at baseline and was abnormal.

Assessments will be made on days -1, 84, 111 and 196, with stand test, and supine and standing catecholamine levels. Symptom surveys COMPASS-31, Quality of Life questionnaire (SF-36), fatigue score, and symptoms score will be repeated at days -14, -1, 84, 98, 111, and 196. The VOSS score will be be performed at screening, baseline, all visits during the washout phase, and at final visit. The analysis will compare responses in the IVIG and placebo groups including individual comparisons between treatment and placebo and group comparisons. A specialized repeated measures analysis will be used to separate the effects of time, treatment and sequence of treatment in this cross-over design.

The primary outcome will be change in COMPASS-31 score (Sletten et al. 2012) (Rea, Campbell, and Cortez 2017). Because both treatments will expand plasma volume, we anticipate that both the IVIG and albumin groups will result in improvement in the COMPASS-31 orthostatic intolerance (OI) subscore. Accordingly, we will analyze the change in both the total COMPASS-31 scores and the score with the OI subscore removed.

Secondary outcomes will be patient subjective responses, reported activity level and objective measures including orthostatic tachycardia, supine and standing catecholamine profiles and skin biopsy results (nerve fiber density). The randomized crossover design will help reduce the confounding factors of interindividual symptom reporting variability and confounding effect of activity level on symptoms and drug carryover from phase 1 to phase 2 of the study. We will subsequently perform post hoc analysis comparing responders to non-responders to determine if baseline characteristics can identify subjects most likely to respond to this intervention.

Our statistician will plan to perform an interim analysis after the first 10 subjects have completed treatment.

The small sample size makes the study sensitive to patient drop out from intolerable side effects or inability to tolerate study design. Patient screening will include careful discussions of the importance of following study protocols. The study includes a 2 week baseline period during which the subjects will follow the study procedures related to daily diary entries to be certain that they are compliant.

Form A

| 4.b. | List of the study intervention(s) being tested or evaluated under this proto                       | ocol  |   |  |  |  |  |  |
|------|--|---|---|--|--|--|--|--|
|      | N/A - this study does not test or evaluate an intervention. Skip to item 4.d.               |   |   |  |  |  |  |  |
| #    | Study intervention(s) being tested or evaluated under the protocol
Add or delete rows as needed | Affiliate
Place a check next to
institution(s) where the
intervention will be
performed | Local Standard
Practice?
Indicate whether the
intervention is
considered
acceptable practice
locally for applicable
institutions |  |  |  |  |  |
|      |  | ⊠ UTSW  | ⊠ Yes   |  |  |  |  |  |
|      |  | PHHS  | □ Yes   |  |  |  |  |  |
| 4    | IVIG infusions   |   | □ Yes   |  |  |  |  |  |
|      | I VIG Infusions  | □THR  | □ Yes   |  |  |  |  |  |
|      |  | □TSRH   | □ Yes   |  |  |  |  |  |
|      |  | □ Other:  | □ Yes   |  |  |  |  |  |
|      |  | ⊠ UTSW  | ⊠ Yes   |  |  |  |  |  |
|      |  |   | □ Yes   |  |  |  |  |  |
| 2    | albumin infusions  |   | □ Yes   |  |  |  |  |  |
| 2    |  | □THR  | □ Yes   |  |  |  |  |  |
|      |  | □TSRH   | □ Yes   |  |  |  |  |  |
|      |  | □ Other:  | □ Yes   |  |  |  |  |  |

**4.c. Risk:Benefit Analysis of study interventions being tested or evaluated under this protocol** For each study intervention identified in section 6b above, complete a risk:benefit analysis table.

(Two tables are provided, copy & paste additional tables as needed or delete both tables if this study does not test an intervention)

| 4.c.
Study Intervention #1
IVIG Infusions  |                  |  |
|--|------------------|--|
| List each group exposed to this
intervention on a separate line.
(e.g., experimental, control, Arm A, Arm B,
etc)
Or state All Groups/Subjects | the intervention | o, list the benefits of this intervention. (Benefits can be directly from
or from a monitoring procedure likely to contribute to the subject's
there are no benefits, state "none". |
| All Groups/Subjects because all subject will get IVIG while in the study   | more stable he   | sion (felling less dizzy/lightheaded), more energetic, less fatigued,
art rate, improve GI &urinary issue associated with POTS, and
erm treatment for POTS                                 |

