Gammunex-C, a form of intravenous immunoglobulin (IVIG), is approved for the treatment of chronic inflammatory demyelinating neuropathy (CIDP) or idiopathic thrombocytopenic purpura (ITP) (see attached package insert). IVIG has been in use for many decades in the treatment of these disorders and many other inflammatory/autoimmune diseases. It is generally very safe and well tolerated. More recently, IVIG has been proposed as an effective treatment for presumed inflammatory neurological disorders which do not meet the criteria for CIDP. Specifically, case reports and cases series have indicated therapeutic responses to IVIG in autonomic neuropathies. (See Goodman, B. P. (2017). "Immunoresponsive Autonomic Neuropathy in Sjogren Syndrome-Case Series and Literature Review." Am J Ther doi: 10.1097/MJT.00000000000583. and Oaklander, A. L. (2016). "Immunotherapy Prospects for Painful Small-fiber Sensory Neuropathies and Ganglionopathies." Neurotherapeutics 13(1): 108-117).

Intravenous Albumin is approved for the treatment of hypovolemia (see attached package insert). The use of albumin to increase plasma volume in patients with POTS has been suggested. In this study, albumin will be used as an active control treatment to provide the same volume and protein load as IVIG but without the immunomodulatory effects.

Significance: There have been few well designed clinical therapy trials aimed at POTS patients and even fewer that are aimed at a particular pathophysiological subtype of POTS. Evidence suggests that POTS is a heterogeneous disorder with differing underlying mechanisms. Several uncontrolled case series have suggested a benefit of IVIG for POTS, but the volume expansion associated with infusion of IVIG make it difficult to assess the immunomodulatory effects of this treatment. We propose to evaluate the efficacy of IVIG using a double-blind randomized cross over design that will determine efficacy while reducing effects of inter-subject variability and placebo effect which are common problems in POTS therapy research. Even with the statistical advantages of a crossover design, the treatment cohort will be small, and this study is designed to be a pilot (phase II) study to evaluate the feasibility, tolerability and potential benefits of treatment. The results of this pilot study will provide the impetus and rationale for a larger multicenter clinical trial to definitively evaluate immunomodulatory treatment in POTS.

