2. Blood testing includes: Complement C3/C4, quantitative immunoglobulins, gAChR, ANA, ENA, APLA, gliadin antibody, transglutaminase antibody, CRP

3. Daily diary will be picked up at every infusion

4. Safety labs: complete blood count (CBC) with differential, basic metabolic panel

5. Skin biopsy is not required. Results can be used if done within the last year. If no results available, PI discretion if biopsy is indicated.

. Repeat skin biopsy assessment if needed can be done between 2-4 weeks after last infusion.

7. Within the past 12 months.

 Collected by online survey via RedCap

\*Patients will follow structured exercise regimen, water and salt recommendations throughout 30 weeks \*Infusion of study drug or albumin would occur on weeks 0, 1, 2, 3, 5, 7, 9, 11 (+/- 2 days) during part 1 and on weeks 17, 18, 19, 20, 22, 24, 26, 28 (+/- 2 days) during part 2. There will be a 6 week washout between weeks 11 and 17 and after week 28. Total study duration of 34 weeks

Abbreviations: complete blood count (CBC), basic metabolic panel (BMP)

\*Clinic visits are highlighted in grey and infusion visits are white

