**a.** Describe the procedures for protecting against or minimizing any potential risks for each of the more than minimal risk research procedures listed above.

Serious side effects of IVIG include renal dysfunction/failure, hemolysis, thrombosis, aseptic meningitis or allergic reaction. Common transient side effects include headache, fatigue, chills, vomiting, back pain, pain, elevated body temperature, abdominal pain, diarrhea, cough, stomach discomfort, chest pain, joint swelling, flu like illness. Each infusion will include standard pre-medications with acetaminophen and cetirizine, and prn medications will be available for headache or nausea at each infusion.

Patients will be able to receive Ondansetron (Zofran) 4mg by mouth every 6 hours PRN for nausea or vomiting.

Vital signs will be taken prior to infusion, at each change of medication, at every rate increase, and at the end of the infusion medication.

All infusions will take place in the CRU infusion unit with experienced and qualified nurses.

Safety labs will be checked on weeks 2, 8, 15 and 24 and include complete blood count (CBC) and complete metabolic panel (CMP). If patient develops a serious side effect or intolerable and persistent common side effect during the treatment phase, infusion will be stopped and they will be considered a treatment failure for that part of the study. If this occurs during Part 1 of the cross-over treatment, these subjects will be allowed to start part 2 after week 12.

**b.** Where appropriate, discuss provisions for ensuring necessary medical or professional intervention in the event of adverse events, or unanticipated problems involving subjects.

Physicians/PI will be available by pager 24/7 and on site during the research infusions. In the case of a serious side effect, subjects will be immediately directed to the appropriate nearest emergency facility.

If the subjects reports any of the following symptoms the infusion nurse will contact the coordinator. Nausea/vomiting, flushing, headache, lightheadedness, and dizziness. The coordinator will inform the PI.

If the subjects any of the following symptoms the infusion nurse will put the stop the infusion and contact the PI and coordinator for an immediate assessment. Chest pain, shortness of breath, swelling, angioedema, rash, any other signs of a serious reaction.

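### Later infusions may start at the tolerated rate with no limit to the same study part, so an albumin-first patient's first IVIG infusion may skip the step-up

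*Protocol*

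**What the plan says.** The infusion procedure in protocol section 4.a sets a stepped start: "Infusion rate will start at 0.6 ml/kg/hour and may be increased by 0.6 ml/kg/hour every 15 min", as tolerated, with a ceiling of 210 ml/hour. It then gives a permission for later infusions: "Subsequent infusion rates may be started at the tolerated rate". Nothing in that sentence refers to the study part or the product.

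Section 4.a also randomises patients to IVIG then albumin, or albumin then IVIG. The notes to the schedule in section 3 place the switch: "There will be a 6 week washout between weeks 11 and 17 and after week 28". Part 2 therefore opens at week 17 (day 119) with the other product. The infusion nurse, patient and coordinator are blinded throughout.

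Section 5.a ties monitoring to the steps: "Vital signs will be taken prior to infusion, at each change of medication, at every rate increase", and again at the end. Section 4.a has vital signs recorded at the start and end of the infusion, at rate changes and when symptoms occur.

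**The concern.** In the IVIG-first group, the first exposure to IVIG is stepped up from 0.6 ml/kg/hour. In the albumin-first group, the first exposure is the ninth scheduled infusion, so on a literal reading it is a later infusion and may start at the tolerated rate. The only rate tolerated by then was on albumin, which says nothing about tolerance of IVIG. The wording thus lets one sequence bypass a precaution that the other receives, along with the vital signs prompted by each rate increase.

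Blinding adds to the point. The nurse cannot tell which patients are meeting IVIG for the first time at week 17, so a restart cannot be applied by product. It has to be written by part and infusion number.

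What is at stake is a safety procedure on one infusion per affected patient. The SAP places phase 2 outside the primary outcome, so the primary comparison and its power do not depend on this. The documents do not link starting rate to the IVIG risks listed in section 5.a, so no harm is asserted.

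**Working it through.** The plan gives no figure on this point to reproduce. The check is a reading of the text plus arithmetic on the protocol's own rates.

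**Inputs from protocol section 4.a:** start and step 0.6 ml/kg/hour; step interval 15 minutes; ceiling 210 ml/hour; dose 0.4 g/kg rounded to the nearest 5 g, as a 10% solution (10 ml per gram).

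**Assumed:** body weight W of 50, 70 or 100 kg, because the documents give none.

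**Formulas**
- Stepped start: s = 0.6 × W ml/hour.
- Largest permitted ratio, if 210 ml/hour is carried over from albumin: 210 / s.
- Increases needed to reach 210 ml/hour: 210 / s rounded up, minus 1.
- Time with step-up: 15 minutes for each rate below 210, then the remaining volume at 210 ml/hour.
- Time without step-up: volume / 210 × 60 minutes.

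| | 50 kg | 70 kg | 100 kg |
|---|---|---|---|
| Dose and volume | 20 g, 200 ml | 28 g rounded to 30 g, 300 ml | 40 g, 400 ml |
| Stepped start s (ml/hour) | 30 | 42 | 60 |
| Rates (ml/hour) | 30, 60, 90, 120, 150, 180, 210 | 42, 84, 126, 168, 210 | 60, 120, 180, 210 (capped) |
| Largest ratio | 210/30 = 7.0 | 210/42 = 5.0 | 210/60 = 3.5 |
| Increases, and so vital-sign checks, passed over | 6 | 4 | 3 |
| Volume given during step-up | 157.5 ml in 90 min | 105 ml in 60 min | 90 ml in 45 min |
| Remainder at 210 ml/hour | 42.5 ml | 195 ml | 310 ml |
| Total with step-up (min) | 102.1 | 115.7 | 133.6 |
| Total at 210 ml/hour throughout (min) | 57.1 | 85.7 | 114.3 |
| Difference (min) | 45.0 | 30.0 | 19.3 |

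**Range at 70 kg, by the rate carried over from albumin**

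| | 42 ml/hour | 126 ml/hour | 210 ml/hour |
|---|---|---|---|
| Ratio to stepped start | 1.0 | 126/42 = 3.0 | 5.0 |
| Volume in first 15 min | 42 × 0.25 = 10.5 ml | 126 × 0.25 = 31.5 ml | 210 × 0.25 = 52.5 ml |
| Share of the 300 ml dose | 3.5% | 10.5% | 17.5% |
| Rate-increase checks passed over | 0 | 2 | 4 |
| Minutes saved by not restarting | 0 | 115.7 − 94.7 = 21.0 | 30.0 |

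The middle column assumes the rate then climbs from 126 through 168 to 210 ml/hour: 31.5 + 42 = 73.5 ml in 30 minutes, then 226.5 ml at 210 ml/hour in 64.7 minutes, 94.7 in all.

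At every weight the lowest case, where only the first step was tolerated on albumin, gives a ratio of 1.0 and no effect.

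**Patients affected:** this cannot be computed. The SAP reports 23 of 30 participants in phase 2 but not how many of them had albumin first.

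**The case against.** The strongest reply is that the paragraph describes a single eight-infusion course. Each patient is scheduled for 16 infusions, yet the same paragraph says "the dose will remain constant for each of the 8 study infusions even if weight changes". The schedule restarts the treatment numbers in part 2. It also repeats eligibility checks on days 105 and 118, history and examination on day 105, and the pregnancy test and safety labs on day 118. On that view the later infusions are numbers 2 to 8 within a part. This reading is plausible, perhaps the more natural one. But the cited phrase governs dose and the rest is scheduling; none of it states a rule for the rate.

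Second, the protocol follows the "infusion center IVIG solution Infusion order" and attaches the IVIG package insert. Either may require a restart, and then the effect is zero. Neither is among the documents, so this remains open.

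Third, the sentence only permits. Everyone changes product at part 2, so a blinded nurse could restart all patients and comply fully. That stands, and it is why this is a gap and not a contradiction.

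Fourth, no vital signs are due where no rate increase occurs, the rate would never exceed the protocol's ceiling, and other safeguards remain: premedication, vital signs at start, end and on symptoms, symptom reporting and stop triggers, a post-infusion coordinator check, an on-site physician and a safety officer. These limit the consequence without supplying a stepped first exposure.

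Finally, the SAP describes phase 2 in the past tense, so a protocol edit may come too late for these patients.

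**Conclusion.** The concern holds as a minor safety clarification. No text in the protocol or SAP confines the tolerated-rate permission to one part or product, so an albumin-first patient's first IVIG infusion may begin without the step-up.

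The 7.0-fold upper figure needs a 50 kg patient, 210 ml/hour tolerated on albumin, staff choosing to carry that rate over, and no contrary rule in the order or insert. Confidence is medium, because the two unseen documents could already settle the matter.

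**What to change.** Replace the sentence with a rule of this kind: *Infusion 1 of each study part starts at 0.6 ml/kg/hour and is stepped up as above; infusions 2–8 of the same part may start at the rate tolerated in that part.* The wording is identical for both sequences, so the nurse needs only the part and infusion number and the blind is kept. Check that the infusion order agrees.

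The cost is one sentence and that check. The added time on one infusion ranges from zero to the differences in the first table, and is zero where staff already restart. If part 2 is complete, read the day 119 starting rates from the existing record ("Start and stop times and infusion rates will be recorded in the study log"), which puts no burden on patients. Then carry the sentence into the larger multicenter trial that this pilot is meant to support.

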## If you are requesting a Waiver of Informed Consent, complete the table below.

#### If you have a consent form, list the reasonably foreseeable risks in the consent form (and do not complete this section).

List the risks according to the probability (likely, less likely or rare) and magnitude (serious or not serious). (include: 1) expected adverse events; 2) rare and serious adverse events; 3) all other psychological, social, legal harms) Do not delete frequency. Frequency must be estimated because it will assist you with determining which adverse events will require prompt reporting.

|   | Not serious | Serious |
|---|--------------------|---------|
| Likely  | •                  | •       |
| These risks are expected to occur in            |                    |         |
| more than 20 out of 100 subjects. |                    |         |
|   | Not serious        | Serious |
| Less likely                                     | •                  | •       |
| These risks are expected to occur in 5-         |                    |         |
| 20 subjects or less out of 100 subjects.        |                    |         |
|   |                    | Serious |
| Rare  |                    | •       |
| These risks are expected to occur in            |                    |         |
| less than 5 subjects out of 100   |                    |         |

| 4.c.
Study Intervention #1
Albumin infusions           |               |   |
|--|---------------|---|
| List each group exposed to this                              |               |   |
| intervention on a separate line. For each gro                |               | , list the benefits of this intervention. (Benefits can be directly from |
| (e.g., experimental, control, Arm A, Arm B, the intervention |               | or from a monitoring procedure likely to contribute to the subject's            |
| etc) well being  |               | here are no benefits, state "none".   |
| Or state All Groups/Subjects                                 |               |   |
| All Groups/Subjects because all subjects will                | Volume expans | sion (felling less dizzy, lightheaded, and fatigued)                            |
| get Albumin while in the study                               |               |   |
|  |               |   |

If you are requesting a Waiver of Informed Consent, complete the table below.

If you have a consent form, list the reasonably foreseeable risks in the consent form (and do not complete this section).

List the risks according to the probability (likely, less likely or rare) and magnitude (serious or not serious).

(include: 1) expected adverse events; 2) rare and serious adverse events; 3) all other psychological, social, legal harms) Do not delete frequency. Frequency must be estimated because it will assist you with determining which adverse events will require prompt reporting.

|   | Not serious | Serious |
|---|-------------|---------|
| Likely  | •           | •       |
| These risks are expected to occur in            |             |         |
| more than 20 out of 100 subjects. |             |         |
|   | Not serious | Serious |
| Less likely                                     | •           | •       |
| These risks are expected to occur in 5-         |             |         |
| 20 subjects or less out of 100 subjects.        |             |         |
|   |             | Serious |
| Rare  |             | •       |
| These risks are expected to occur in            |             |         |
| less than 5 subjects out of 100                 |             |         |

|   |  | The combination procedures that will  | nents not listed in table 4.b.
uld account for all of the research
dy.
gle component (e.g., blood work, CT = safety  |  |
|---|--|---|--|--|
| # | Research component   • individual procedures   example:   Eligibility Assessments   • History and physical   • Questionnaire   • Laboratory tests   Add or delete rows as needed | Column A
Local Standard
Practice Indicate the
number of times each
procedure will be
performed as stipulated
in the research plan that
would be performed if
the participant were not
participating in the
study. | Column B
Research Only
Indicate the number of times
each procedure will be
performed solely for research
purposes (meaning that the
participant would not undergo
the same number of
procedures or would not
undergo the procedure(s) at
the same frequency if they
were not participating in the
study) | Column D
Risks
If you are requesting a Waiver of Informed
Consent, complete the table below.
List the reasonably expected risks for each procedure
or group of procedures under the following categories
as appropriate:
• Serious and likely;
• Serious and less likely;
• Serious and rare;
• Not serious and likely;
• Not serious and less likely |
| 1 | Eligibility Assessments  |   |  |  |
|   | Medical History  | 1   | 1  |  |
|   | VitalSigns/Physical Exam   | 1   | 1  |  |
|   | Autonomic Testing  | 1   | 2  |  |
|   | Skin Biopsy  | 1   | 2  |  |
|   | Labs   | 1   | 5  |  |
|   | Pregnancy test   | 0   | 2 3  |  |
|   | Supine & Standing
Catecholamines  |   | 3  |  |
|   | QoL questionnaire  | 1   | 7  |  |
|   | Compass Change score   | 0   | 16   |  |
|   | COMPASS 31   | 1   | 7  |  |
|   |  |   |  |  |
| 2 | Patient Responsibilities   |   |  |  |
|   | Daily Diary (Fluid & Exercise)   | 17  |  |  |
|   | Symptom Score  | 0   | 8  |  |
|   | Side effect form   | 0   | 8  |  |
|   | Subject Impression
Questionnaire  | 0   | 8  |  |
| 3 |  |   |  |  |
|   | Insert procedure here  |   |  |  |
|   | Insert procedure here  |   |  |  |
|   | Insert procedure here  |   |  |  |
| 4 |  |   |  | ļ  |
|   | Insert procedure here  |   |  |  |
|   | Insert procedure here  |   |  |  |
|   | Insert procedure here  |   |  |  |
|   |  |   |  |  |
|   |  |   | l  |  |

| IRB # | STU 2018-0005 |
|-------|---------------|
|-------|---------------|

| 5. Sa | ety Precautions. | (Describe safeguards to address the serious risks listed above.) | ) |
|-------|------------------|--|---|
|-------|------------------|--|---|

**a.** Describe the procedures for protecting against or minimizing any potential risks for each of the more than minimal risk research procedures listed above.

Serious side effects of IVIG include renal dysfunction/failure, hemolysis, thrombosis, aseptic meningitis or allergic reaction. Common transient side effects include headache, fatigue, chills, vomiting, back pain, pain, elevated body temperature, abdominal pain, diarrhea, cough, stomach discomfort, chest pain, joint swelling, flu like illness. Each infusion will include standard pre-medications with acetaminophen and cetirizine, and prn medications will be available for headache or nausea at each infusion.

Patients will be able to receive Ondansetron (Zofran) 4mg by mouth every 6 hours PRN for nausea or vomiting.

Vital signs will be taken prior to infusion, at each change of medication, at every rate increase, and at the end of the infusion medication.

All infusions will take place in the CRU infusion unit with experienced and qualified nurses.

Safety labs will be checked on weeks 2, 8, 15 and 24 and include complete blood count (CBC) and complete metabolic panel (CMP). If patient develops a serious side effect or intolerable and persistent common side effect during the treatment phase, infusion will be stopped and they will be considered a treatment failure for that part of the study. If this occurs during Part 1 of the cross-over treatment, these subjects will be allowed to start part 2 after week 12.

**b.** Where appropriate, discuss provisions for ensuring necessary medical or professional intervention in the event of adverse events, or unanticipated problems involving subjects.

Physicians/PI will be available by pager 24/7 and on site during the research infusions. In the case of a serious side effect, subjects will be immediately directed to the appropriate nearest emergency facility.

If the subjects reports any of the following symptoms the infusion nurse will contact the coordinator. Nausea/vomiting, flushing, headache, lightheadedness, and dizziness. The coordinator will inform the PI.

If the subjects any of the following symptoms the infusion nurse will put the stop the infusion and contact the PI and coordinator for an immediate assessment. Chest pain, shortness of breath, swelling, angioedema, rash, any other signs of a serious reaction.

In the case of any unanticipated problems, the research pharmacist (who is unblinded to treatment allocations) may consult with [name] (an autonomic disorders expert who is not involved with research assessments) who has agreed to serve as the safety officer for this study. [name] will be responsible for review of abnormal safety labs or adverse events to determine if a patient should be withdrawn from the study for safety reasons.

| c. Will the safeguards be different between/among groups? |   |    |  |  |  |  |
|---|---|----|--|--|--|--|
| Yes   | V | No |  |  |  |  |
| If yes, describe here                                     |   |    |  |  |  |  |
